5.3.3. Concomitant Medications

Previous and concomitant medications will be coded using the World Health Organization (WHO) Drug Dictionary Enhanced September 2017 version. Previous and concomitant medications will be presented in a data listing. Concomitant medications will additionally be summarized by aggregate treatment group.

Missing end dates will be imputed as previously outlined in [Section 3.3.5](#) as required to determine concomitant medications, and all ongoing medications will be considered concomitant.

6. PROTOCOL DEVIATIONS

Possible protocol deviations will be identified and displayed in a data listing and sorted by subject, Period, and study day (where applicable). An additional listing of those deviations deemed Major during the blinded review will be provided.

7. CHANGES IN THE PLANNED ANALYSES

The following secondary endpoints listed in the protocol were removed, with replacements noted in parenthesis.

- Change in serum ALP between Baseline and Weeks 12 or 18, dependent upon the length of continuous treatment, compared to the placebo response during Period 1 (replaced with change from Week 6 to Week 12, and Week 12 to Week 18);

endpoint will be evaluated from descriptive summaries, but no statistical testing will be performed)

- Change in serum ALP between a new baseline at Week 6 and the final value at Weeks 12 for those subjects who received placebo during Period 1, compared to their initial 6-week placebo response (endpoint will be evaluated from descriptive summaries, but no statistical testing will be performed)
- Change in serum ALP between a new baseline at Week 6 and the final value at Weeks 12 for those subjects who received placebo during Period 1, compared to the similar change in the 500 mg and 1,000 mg treatment groups (endpoint will be evaluated from descriptive summaries, but no statistical testing will be performed)
- Change in serum ALP between a new baseline at Week 12 and the final value at Weeks 18 for all subjects following the randomized withdrawal (endpoint will be evaluated from descriptive summaries, but no statistical testing will be performed)
- Proportion of patients who achieve ALP of $<1.5 \times \text{ULN}$ (endpoint will be evaluated from descriptive summaries, but no statistical testing will be performed)
- Proportion of patients who achieve a 50% decrease in ALP (endpoint will be evaluated from descriptive summaries, but no statistical testing will be performed)
- The proportion of patients who normalize ALP (endpoint will be evaluated from descriptive summaries, but no statistical testing will be performed)
- Change in AST/ALT ratio (endpoint replaced with change in GGT)
- Change in serum bilirubin (endpoint will be evaluated from descriptive summaries, but no statistical testing will be performed)
- In subjects with IBD who have elevated fecal calprotectin (FC), change in FC compared to Baseline at Weeks 6 and 12, and the proportion of subjects who normalize FC at Weeks 6 and 12 (change in FC will be evaluated for all subjects with IBD, not just those with elevated FC; both endpoints will evaluated from descriptive summaries but no statistical testing will be performed)
- For subjects who have elevated CRP at Baseline (for all subjects In the IBD subset): change from Baseline in CRP at Weeks 6 and 12, and normalization of CRP at Weeks 6 and 12 (change in CRP will be evaluated for all subjects with IBD, not just those with elevated CRP; both endpoints will evaluated from descriptive summaries but no statistical testing will be performed)
- For subjects with IBD who have Partial Mayo score above 0: Change from Baseline in Mayo scores at Weeks 6 and 12. (For Week 12, change from Week 6 will replace change from baseline; endpoint will evaluated from descriptive summaries but no statistical testing will be performed)

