The mITT population will be used for the analysis of all efficacy endpoints. The primary efficacy variable is the change in ALP from Baseline to Week 6 in the initial double-blind parallel group period. Changes in ALP from Baseline will be summarized by treatment group, visit and treatment period using descriptive statistics. A mixed model repeated measures (MMRM) will be fit to the data and the model will include fixed factors for treatment, visit and treatment by visit interaction, a random factor for subject, and Baseline value as a covariate. An unstructured covariance matrix will be used to model the repeated assessment over time. Denominator degrees of freedom will be adjusted using Kenward-Roger's method. Sensitivity analyses will be described in the statistical analysis plan (SAP). Treatment comparisons will be made at each visit and each treatment period, with the primary comparison at Week 6. No imputation of missing data is necessary for the MMRM analysis of the primary endpoint. A similar MMRM analysis will be performed for the randomized withdrawal period. Analysis for the randomized withdrawal period will be conducted for all subjects and separately for responders based on pre-specified responder criteria. For the dose-controlled treatment period, a one sample t-test will be used to evaluate the change in ALP from Week 6 to Week 12 for the subjects who were previously randomized to placebo during the first period.

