Population PK models for the components of HTD1801 will be developed and validated using a nonlinear mixed-effects model (NONMEM) approach. Selection of the appropriate model will be based on hypothesis testing and graphical analysis of residual error (goodness of fit). Target parameters for each component include apparent clearance (CL/F) and apparent volume of distribution at steady state (V_{ss}/F). Covariate relationships will be evaluated and incorporated into the model as indicated by the data. Covariates for evaluation will include, but will not be limited to, vital signs (e.g., body size), demographics (e.g., sex, age, race) and organ function / disease biomarkers (e.g., bilirubin and alkaline phosphatase). The models will be validated using likelihood profiles, bootstrap analysis, and visual predictive check.

Concentration vs. time profiles will be simulated for each subject based on that subject's individual-specific (post-hoc) parameter estimates. Individual single-dose and steady-state non-compartmental metrics will be calculated from these simulated data. Metrics for UDCA will be reported with and without baseline correction.

Pharmacokinetic/Pharmacodynamic Analysis

An exploratory exposure-response analysis will be performed to evaluate the relationship between exposure metrics (e.g., AUC, C_{max}) for UDCA, BBR, and UDCA+BBR and change from baseline in serum ALP. The analysis will evaluate the effect of covariates including disease state (e.g., baseline ALP; IBD with elevated FC; elevated CRP).

An exploratory exposure-response analysis will be performed to evaluate the relationship between exposure, adverse events (AE) of interest, and serious adverse events (SAE). The relationship between exposure and AE or SAE occurrence will be evaluated graphically and, where indicated, statistically.

Name of sponsor company: HighTide BioPharma Pty. Ltd.

Name of finished product: HTD1801 Tablets

Name(s) of active ingredient(s): Berberine Ursodeoxycholate (HTD1801)

Study Design: The entire study is randomized and double blind, with a concurrent placebo control except in Period 2. Randomization will be stratified based on presence of IBD.

Period 1: Placebo and dose controlled (6 weeks)

Each subject will be randomized to one of three groups: a) placebo twice daily with food; b) 500 mg of HTD1801 twice daily with food; or c) 1000 mg of HTD1801 twice daily with food.

Period 2: Dose-controlled extension (6 weeks)

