8.2.3 Efficacy Analysis

The mITT population will be used for the analysis of all efficacy endpoints. No alpha adjustments for multiplicity will be made for the analysis of efficacy endpoints for this proof of concept study.

The primary efficacy variable is the change in ALP from Baseline to Week 6 in the double-blind parallel group period. Changes in ALP from Baseline will be summarized by treatment group and visit using descriptive statistics. A mixed model repeated measures (MMRM) will be fit to the data and the model will include fixed factors for treatment, randomization strata of IBD diagnosis, visit and treatment by visit interaction, and Baseline value as a covariate. An unstructured covariance matrix will be used to model the repeated assessment over time. Denominator degrees of freedom will be adjusted using Kenward-Roger's method. Sensitivity analyses will be described in the statistical analysis plan (SAP). Treatment comparisons will be made at each visit,

with the primary comparison at Week 6. No imputation of missing data is necessary for the MMRM analysis of the primary endpoint. A similar MMRM analysis will be performed for the randomized withdrawal period. Analysis for the randomized withdrawal period will be conducted for all subjects and separately for responders based on pre-specified responder criteria. For the dose-controlled treatment period, a one sample t-test will be used to evaluate the change in ALP from Week 6 to Week 12 for the subjects who were previously randomized to placebo during the first period.

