Following their completion of Period 1, subjects will enroll in a 6-week extension period in which subjects previously randomized to 500 mg or 1000 mg BID will continue for 6 more weeks at that previous dose, while subjects previously randomized to placebo will be randomly assigned to receive 6 weeks of either 500 mg or 1000 mg BID.

Period 3: Randomized withdrawal

Following their completion of Period 2, subjects will enroll into a 6-week randomized withdrawal period in which all subjects will be randomly assigned in a 1 to 1 ratio to either continue on the active treatment they received in Period 2, or be assigned to placebo so that 50% of the subjects remain on the experimental treatment at the previous dose, and 50% will receive placebo.

All subjects and study personnel will remain blinded as to the treatment administered throughout the study with the exception of an unblinded statistician who will develop the randomization list with the expanded strata and an unblinded EDC designer who will load the completed randomizations

into the EDC system. All study test drug will be provided in matching white tablets, four to a bottle, two bottles to be administered each day, one in the morning and one in the evening. A 45-day supply will be provided to each subject at each visit to cover the next 6-week period with an additional 3 days of coverage to provide for possible scheduling conflicts.

In this double-blind study, if a medical emergency occurs and a decision about a subject's condition requires knowledge of the treatment assignment in order to properly treat the subject, the study blind may be broken for that specific subject only. Ideally, the decision to break the blind for this one subject should only be made after consultation with the Medical Monitor or Sponsor Representative.

Any broken blind must be clearly justified and explained by a note in the subject's source documents.

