3.3. HANDLING OF DATA

3.3.1. Strata and Covariates

Statistical models run for the primary endpoint as well as secondary continuous endpoints in Period 1 will include IBD diagnosis as randomized and UDCA status when entering the study as covariates. Secondary continuous endpoints in Periods 2 and 3 will also include IBD diagnosis and UDCA status as a covariate.

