5.2.4. Secondary Efficacy Endpoints

- Relative change in ALP from Baseline to Week 6
- Absolute change in ALP from Week 6 to Week 12
- Change in ALP from Week 12 to Week 18 for all subjects following the randomized withdrawal
- Proportion of subjects who achieve ALP of $< 1.5 \times \text{ULN}$ at the end of each period for each treatment group

- Proportion of subjects who achieve at least a 50% decrease in ALP at the end of each period for each treatment group
- Proportion of subjects who normalize ALP at the end of each period for each treatment group
- Absolute change in Gamma-Glutamyl Transferase (GGT) from Baseline to Week 6
- Relative change in GGT from Baseline to Week 6
- Absolute change in GGT from Week 6 to Week 12
- Change in GGT from Week 12 to Week 18 for all subjects following the randomized withdrawal
- Absolute change in serum total bilirubin at the end of each period for each treatment group
- In subjects with IBD, absolute change in fecal calprotectin (FC) from Baseline to Week 6
- In subjects with IBD, absolute change in FC from Week 6 to Week 12
- In subjects with IBD, absolute change in FC from Week 12 to Week 18 for all subjects following the randomized withdrawal
- In subjects with IBD who have elevated FC, the proportion of subjects who normalize FC at Weeks 6, 12, and 18 for each treatment group
- In subjects with IBD, absolute change in C-reactive Protein (CRP) from Baseline to Week 6
- In subjects with IBD, absolute change in CRP from Week 6 to Week 12
- In subjects with IBD, absolute change in CRP from Week 12 to Week 18 for all subjects following the randomized withdrawal
- In subjects with IBD who have elevated CRP, the proportion of subjects who normalize CRP at Weeks 6, 12, and 18 for each treatment group
- In subjects with IBD, absolute change in Mayo scores from Baseline to Week 6
- In subjects with IBD, absolute change in Mayo scores from Week 6 to Week 12
- In subjects with IBD, absolute change in Mayo scores from Week 12 to Week 18 for all subjects following the randomized withdrawal
- In subjects with IBD who have Baseline Partial Mayo score above 0, absolute change in Mayo scores from Baseline to Week 6
- In subjects with IBD who have Baseline Partial Mayo score above 0, absolute change in Mayo scores from Week 6 to Week 12
- In subjects with IBD who have Baseline Partial Mayo score above 0, absolute change in Mayo scores from Week 12 to Week 18 for all subjects following the randomized withdrawal

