5.2.5. Secondary Efficacy Analysis

All secondary endpoints will be summarized descriptively by treatment group and visit as defined for each period. Continuous endpoints will present baseline and actual value summaries and change from baseline (Period 1), Week 6 (Period 2), or Week 12 (Period 3) as appropriate. Proportions will be presented with denominators based on the number of subjects randomized to each treatment group.

The mean ALP values will additionally be represented graphically via a line chart for Period 2 and Period 3, with one page for each treatment group, with a line for each subject within the group charted individually, and with one line for the overall group. Period 2 will graph values for all scheduled visits from Baseline through Week 12 and Period 3 will graph values for all scheduled visits from Baseline through Week 18.

Absolute change in GGT from Baseline to Week 6 will be tested using a mixed model with repeated measures (MMRM) analogous to the primary endpoint ([Section 5.2.2](#)). This model will include fixed effects for treatment, IBD diagnosis, UDCA status, visit and treatment by visit interaction, with Baseline GGT value as a covariate. An unstructured covariance matrix will be used to model the repeated assessments over time. Denominator degrees of freedom will be adjusted using Kenward-Roger's method. Least Square (LS) Means and corresponding standard errors and 95% confidence intervals resulting from the model described will be presented at each visit. Differences in LS Means and corresponding two-sided 95% confidence intervals will be calculated at each visit comparing each active arm to placebo as well as comparing the HTD1801 1000 mg BID treatment group to the HTD1801 500 mg BID treatment group. The primary comparison of these treatment groups will be at Week 6.

Absolute change in GGT from Baseline to Week 6 will also be summarized by the subgroups as detailed in [Section 5.2.3](#).

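### The SAP leaves the randomised-withdrawal placebo comparison of ALP with no prespecified adjusted difference or confidence interval, and gives no reason for dropping the protocol's model

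*SAP*

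**What the plan says.** **Protocol.** Section 8.2.3 says of ALP: "A similar MMRM analysis will be performed for the randomized withdrawal period". The synopsis and 8.2.3 both add: "Analysis for the randomized withdrawal period will be conducted for all subjects and separately for responders based on pre-specified responder criteria". Section 8.2.3 also plans, for the same period, an analysis of the ALP proportions similar to the Fisher's exact comparison at Week 6. On the control group, the synopsis says: "The entire study is randomized and double blind, with a concurrent placebo control except in Period 2".

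**SAP.** Section 3.2 keeps the re-randomisation: "all subjects will be randomly assigned in a 1 to 1 ratio to either continue on the active treatment they received in Period 2", or to move to placebo. Section 5.2.4 keeps the endpoint on the secondary list: "Change in ALP from Week 12 to Week 18 for all subjects following the randomized withdrawal". Section 5.2.5 then says "All secondary endpoints will be summarized descriptively by treatment group and visit as defined for each period", and the only secondary model it specifies is for GGT in Period 1. Section 7 repeats that the Week 12 to Week 18 ALP change will not be tested: "for all subjects following the randomized withdrawal (endpoint will be evaluated from descriptive summaries, but no statistical testing will be performed".

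Two other SAP passages point the other way. Section 3.3.1 says: "Secondary continuous endpoints in Periods 2 and 3 will also include IBD diagnosis and UDCA status as a covariate". Section 5 names unpaired and paired t-tests and Fisher's exact test among the methods, but no efficacy section assigns them to an endpoint.

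**The concern.** Most secondary endpoints were made descriptive, and for many of them little is lost. Period 3 is different. The Period 2 changes have no concurrent placebo group, whereas Period 3 is double-blind, re-randomised 1:1 and placebo-controlled. Its Week 18 comparison of continued treatment with placebo is the only randomised placebo evidence on the primary biomarker after Week 6.

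As written, a reader would have to form that comparison from separate group summaries. The Period 3 groups in SAP 5 include a pooled All Active to Placebo group but no pooled continued-active group to set against it. An adjusted contrast could still be produced later, but its model, covariates and pooling would then be chosen after the data were seen. Meanwhile SAP 3.3.1 assumes a Period 3 model that no section defines, so two programmers could reasonably build different outputs.

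**Working it through.** **1. Text side by side**

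| Item | Protocol synopsis / 8.2.3 | SAP |
|---|---|---|
| Period 3 ALP change, all subjects | MMRM | Descriptive (5.2.5, 7); no reason given |
| Period 3 ALP change, responders | Separate analysis | Absent; not listed in 7 |
| Period 3 ALP proportions | Analysis similar to Week 6 Fisher's test | Descriptive; 7 rules out testing without naming the period or test |
| Covariates for Period 3 continuous endpoints | MMRM similar to Period 1 | IBD and UDCA (3.3.1), with no model to hold them |
| Between-group difference or CI | Available from the MMRM | None: SAP 5 defines descriptive statistics as n, mean, median, SD, minimum and maximum |

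**2. The plan's own figures (Period 1 only)**

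Inputs from SAP 3.1: SD of change from Baseline 200, two-sided alpha 0.05, 80% power. By the two-sample noncentral t:
- 30 per group detects 147.1, against 147 stated; 147/450 = 32.7%, as stated.
- 21 per group detects 177.2, and power for the stated 180 is 81.2%.

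Both figures reproduce. Neither document gives a power or precision figure for Period 3.

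**3. Illustrative Period 3 precision**

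SAP 3.2 gives 42 + 17 = 59 subjects randomised. SAP 1.1 mentions 3 randomised but not dosed; if they are among the 59, then 56 remain, or 28 per arm at 1:1. I assume that no one is lost and that SD 200 carries over to the Week 12 to Week 18 change.

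Half-width of the 95% CI = t(0.975, 2n−2) × SD × √(2/n).

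| Comparison | SD | Half-width (U/L) | Detectable at 80% power (U/L) |
|---|---|---|---|
| Pooled, 28 v 28 | 200 | 107.2 | 152.5 |
| Pooled, 22 v 22 | 200 | 121.7 | 172.9 |
| One dose, 14 v 14 | 200 | 155.4 | 220.0 |
| Pooled, 28 v 28 | 100 | 53.6 | 76.2 |
| Pooled, 28 v 28 | 250 | 134.0 | 190.6 |

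**4. What adjustment for Week 12 ALP would gain**

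Adjusted half-width ≈ 107.2 × √(1 − r²), where r is the assumed correlation, in absolute value, of Week 12 ALP with the later change:
- r = 0.3: 102.2
- r = 0.5: 92.8
- r = 0.7: 76.5

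This is a gain of about 5% to 29%.

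**5. What a chance imbalance in Week 12 ALP would do**

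The endpoint is already change from Week 12. An imbalance therefore enters only through the slope of the change on Week 12 ALP:

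shift = r × (imbalance in SDs of Week 12 ALP) × SD of change.

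For 0.25 SD: 0.3 × 0.25 × 200 = 15 U/L and 0.7 × 0.25 × 200 = 35 U/L, against the half-width of 107.

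Without stratification on ALP, the standardised difference has standard error √(2/28) = 0.267. An imbalance of at least 0.25 SD then has probability about 0.35, and of at least 0.5 SD about 0.06.

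**The case against.** The best defence is that this is a disclosed choice in a small proof-of-concept study. SAP 7 announces it and treats nearly every secondary endpoint the same way. The primary analysis rests on Period 1, the sample size was cut to about 60, and enrolment stopped early. Group n, mean and SD will be tabulated, so a reader can compute an unadjusted difference and interval. Much of this stands: nothing is concealed, and forgoing p-values is defensible. It does not explain forgoing an estimate. An interval computed afterwards would be crude and not prespecified. Nor is small size a clear reason: at SD 200, 22 v 22 (about a quarter of 59 lost) detects 173, and SAP 3.1 accepted 180 for Period 1.

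A reader might infer that a chance imbalance in Week 12 ALP passes straight into the crude comparison, or that the 35% above is the chance of a material bias. Neither follows. Week 12 ALP is already subtracted, and 35% is the frequency of an imbalance of that size, not of its effect on the result.

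A reader might also infer that the Period 3 re-randomisation is unstratified. The documents do not settle this. SAP 3.2 ties the UDCA stratum to Period 1, yet the protocol synopsis states IBD stratification without limiting it to a period, and SAP 3.2 mentions expanded strata in text covering the whole study. Stratification by dose, UDCA or ALP is simply not clearly stated.

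Finally, a model pooled over dose should not be taken as a restoration of the protocol's analysis. An MMRM similar to Period 1 would keep the doses apart, so pooling is a new supportive contrast.

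**Conclusion.** The point holds as one of prespecification and consistency. The protocol's Period 3 MMRM is replaced by summaries that contain no treatment difference or interval. No reason is given, the loss of the responder analysis is unrecorded, and SAP 3.3.1 and 5 do not agree with 5.2.5 and 7.

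The cost is that any adjusted Period 3 contrast would be post hoc, and that the crude one is less precise: about ±107 U/L rather than about ±102 to ±77. A 0.25 SD imbalance in Week 12 ALP would shift the crude contrast by about 15 to 35 U/L. All of these figures assume SD 200 for the Week 12 to Week 18 change, 28 per arm, no attrition and r between 0.3 and 0.7. The documents supply none of these for Period 3, so the figures are illustrations. The primary Week 6 analysis is untouched. This is a cheap improvement, not a flaw that threatens the trial's main conclusion.

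**What to change.** In SAP 5.2.5 and 7, specify one supportive MMRM of ALP change from Week 12 at Weeks 14, 16 and 18:
- **Subjects:** those re-randomised at Week 12 with at least one later ALP value, analysed as assigned.
- **Model:** fixed effects for Period 3 assignment (continue or placebo), Period 2 dose, IBD, UDCA, visit and assignment-by-visit; Week 12 ALP as covariate; unstructured covariance; Kenward-Roger degrees of freedom.
- **Report:** the Week 18 continue-versus-placebo difference with its 95% CI and no formal testing claim. Say that pooling over dose is a new supportive contrast chosen for precision. Keep by-dose results descriptive.

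In SAP 5, add a pooled All Active to Active group to match All Active to Placebo, and remove listed tests that no analysis uses. Limit the SAP 3.3.1 covariate sentence to endpoints that have a model. In SAP 7, give the reason for the change and record by name that the responder MMRM and the Period 3 Fisher comparisons are dropped. State whether the Period 3 re-randomisation is stratified, and by what.

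The cost is SAP wording and one model adapted from the Period 1 code, settled before unblinding. ALP is already scheduled at these visits, so no new data are needed. The downside is one more supportive comparison without multiplicity adjustment.

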3.3.1.2 Secondary Endpoints

The secondary endpoints of this study include the following:

- 1. Change in serum ALP between Baseline and Weeks 12 or 18, dependent upon the length of continuous treatment, compared to the placebo response during Period 1;
- 2. Change in serum ALP between a new baseline at Week 6 and the final value at Weeks 12 for those subjects who received placebo during Period 1, compared to their initial 6-week placebo response;
- 3. Change in serum ALP between a new baseline at Week 6 and the final value at Weeks 12 for those subjects who received placebo during Period 1, compared to the similar change in the 500 mg and 1,000 mg treatment groups;
- 4. Change in serum ALP between a new baseline at Week 12 and the final value at Weeks 18 for all subjects following the randomized withdrawal;
- 5. Proportion of patients who achieve ALP of $\leq 1.5 \times \text{ULN}$;
- 6. Proportion of patients who achieve a 50% decrease in ALP;
- 7. The proportion of patients who normalize ALP;
- 8. Change in AST/ALT ratio;
- 9. Change in serum bilirubin;
- 10. In subjects with IBD who have elevated fecal calprotectin (FC), change in FC compared to Baseline at Weeks 6 and 12, and the proportion of subjects who normalize FC at Weeks 6 and 12;
- 11. For subjects who have elevated CRP at Baseline (for all subjects In the IBD subset): change from Baseline in CRP at Weeks 6 and 12, and normalization of CRP at Weeks 6 and 12.
- 12. For subjects with IBD who have Partial Mayo score above 0: Change from Baseline in Mayo scores at Weeks 6 and 12.

Clinical Protocol

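### The SAP widens fecal calprotectin and CRP change to all IBD subjects and drops the protocol's elevated-value subset; that subset should be shown beside the all-IBD summaries

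*SAP*

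**What the plan says.** Protocol 3.3.1.2 ties both biomarker changes to subjects with elevated values. For FC: "In subjects with IBD who have elevated fecal calprotectin (FC), change in FC compared to Baseline at Weeks 6 and 12". For CRP: "For subjects who have elevated CRP at Baseline (for all subjects In the IBD subset): change from Baseline in CRP at Weeks 6 and 12".

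SAP section 7 widens both populations. For FC, "change in FC will be evaluated for all subjects with IBD, not just those with elevated FC"; for CRP, "change in CRP will be evaluated for all subjects with IBD, not just those with elevated CRP". It states that these endpoints will be described and not tested, and gives no reason for the wider population.

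The endpoint list in SAP 5.2.4 follows suit: "In subjects with IBD, absolute change in fecal calprotectin (FC) from Baseline to Week 6" and "In subjects with IBD, absolute change in C-reactive Protein (CRP) from Baseline to Week 6", then Week 6 to 12 and Week 12 to 18. No change endpoint for either marker is restricted to elevated subjects. The same list keeps the restriction for normalization, for example "In subjects with IBD who have elevated FC, the proportion of subjects who normalize FC at Weeks 6, 12, and 18". It also shows Partial Mayo change twice, once for all IBD subjects and once for an active subset: "In subjects with IBD who have Baseline Partial Mayo score above 0, absolute change in Mayo scores from Baseline to Week 6".

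**The concern.** Concurrent IBD activity is the only secondary efficacy objective (Protocol 2.0, SAP 2). Entry leans toward controlled disease: Partial Mayo 0 to 4, stable IBD medication, no severe active IBD and no recent flare that needed more therapy (Protocol 3.2.1 and 3.2.2). Some IBD subjects may therefore start with normal FC or CRP and have little room to fall.

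Averaging over them has two effects. The mean change moves toward zero by an amount that depends on case mix. And since SAP 5.2.5 specifies a model only for GGT, the FC and CRP arm means are unadjusted. A chance difference between arms in the elevated share then feeds into the comparison, because elevated subjects tend to drift down untreated.

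The SAP already reports Mayo change both ways, so leaving the subset out for FC and CRP change alone is an unexplained inconsistency. What is at stake is the size and reading of a descriptive estimate.

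**Working it through.** **Plan's own figure.** There is none for FC or CRP. The sample-size figures in both documents concern ALP and do not bear on this point. All numbers below other than the count randomized are assumptions, shown over a range.

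**1. Dilution.** Let *f* be the share of IBD subjects with an elevated Baseline value and *d* the effect in them, with no change in the rest. Then

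all-IBD mean effect = *f* × *d* + (1 − *f*) × 0 = *f* × *d*.

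For *f* = 0.3, 0.5 and 0.7 this is 30%, 50% and 70% of *d*. A fall of 100 units would appear as −30, −50 or −70.

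**2. Signal-to-noise.** The loss here is smaller than the dilution. Take the SD in elevated subjects as 1, the SD in the others as *s*, and *d* = 0.8. Per IBD subject per arm:

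- treated-arm variance: *f* + (1 − *f*)*s*² + *f*(1 − *f*)*d*²
- placebo-arm variance: *f* + (1 − *f*)*s*²
- all-IBD ratio: *fd* / √(sum of the two variances)
- elevated-only ratio: *d*√*f* / √2

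All-IBD divided by elevated-only:

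| *f* | *s* = 1 | *s* = 0.25 |
|---|---|---|
| 0.3 | 0.53 | 0.85 |
| 0.5 | 0.68 | 0.90 |
| 0.7 | 0.81 | 0.94 |

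Check at *f* = 0.5, *s* = 1: 0.4/√(1.16 + 1) = 0.272, and 0.8 × 0.707/1.414 = 0.400, so the ratio is 0.68. The loss is about 19% to 47% with equal SDs, and about 6% to 15% if normal-value subjects vary little.

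**3. Subjects available.** SAP 3.2 gives 42 + 17 = 59 randomized, or 19.7 per arm. With an assumed IBD share of 50% to 80% there are 9.8 to 15.7 IBD subjects per arm. With *f* from 0.3 to 0.7, the number elevated per arm runs from 0.3 × 9.8 = 3 to 0.7 × 15.7 = 11. If the three subjects who were randomized but not dosed (SAP 1.1) are among the 59, 56 remain and the range is 2.8 to 10.5.

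**4. Chance imbalance.** Assume 13 IBD subjects per arm and *f* = 0.5. A gap in shares of 20 points or more needs a count difference of at least 3, since 2/13 = 15% and 3/13 = 23%. The probability is 2 × P(Bin(26, 0.5) ≤ 10) = 0.33. If elevated subjects drift down 60 units untreated, a 60% v 40% split shifts the arm difference by −60 × (0.6 − 0.4) = −12 with no drug effect. The sign is equally likely to go the other way.

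**5. The same drift in the subset.** Within an elevated-only arm the assumed drift is the full −60, against −30 in the all-IBD mean at *f* = 0.5. It is expected in both arms, so in Period 1 it cancels on average in the comparison with placebo, but not in the within-arm change.

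**The case against.** Much of the case for leaving the SAP alone stands. The change is disclosed. FC and CRP are descriptive, so no test loses power and no decision rule depends on them. SAP 5.2.5 puts baseline and actual values beside the change, so an imbalance between arms could be seen. The wider population also has merit: subjects with normal values can worsen, including after withdrawal, and an elevated-only set cannot show that. The subset would be small and more exposed to regression to the mean.

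A reader might go further and infer that the IBD objective is now measured mainly in subjects who cannot improve, so that a real benefit would be hidden. The documents do not support that. Neither gives the share with elevated FC or CRP. The entry rules limit symptoms, physician assessment and recent therapy but set no FC or CRP limit, and a Partial Mayo of up to 4 allows some activity. Three measures in subjects able to improve remain: FC normalization, CRP normalization, and Mayo change in those scoring above 0.

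These points lower the priority without removing the gap. With no test, the size of the mean change is itself the result. Normalization is a yes/no threshold that misses large falls ending above normal, and Partial Mayo records symptoms and physician assessment, not a biomarker. Because the proposal adds a summary and replaces nothing, the value of seeing worsening in normal-value subjects is kept.

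**Conclusion.** The concern holds as a minor one. The SAP drops a protocol-defined analysis population for two endpoints without a reason, and treats FC and CRP change differently from Mayo change and from its own normalization endpoints. Whenever some IBD subjects have normal Baseline values and change little, the all-IBD mean understates the change in elevated subjects: it shows 30% to 70% of it for an assumed elevated share of 30% to 70%. Chance imbalance in that share can move unadjusted arm means in either direction; it is noise and not a directional bias. The actual size cannot be stated, because the elevated share, the IBD share and the FC and CRP variability are not in the documents. The harm is to interpretation of a descriptive estimate. It does not extend to the primary analysis, to any test, or to the IBD objective as a whole.

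**What to change.** Keep the all-IBD summaries. In SAP 5.2.4, add beside them FC change and CRP change in IBD subjects elevated at Baseline, from Baseline to Week 6 and from Baseline to Week 12. These are the protocol's time points and reference; SAP 5.2.4 currently measures Week 12 from Week 6.

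State one definition of elevated, for example above the laboratory's upper limit of normal, and use it for both change and normalization. Neither document defines the term, and the protocol ties it to Baseline for CRP but not for FC. Show the number elevated per arm in each table.

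Period 3 summaries in this subset would be new, because the protocol endpoint stops at Week 12; they are optional.

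The cost is a few extra tables on a subset that normalization already requires. Counts will be small, about 3 to 11 per arm in Period 1 under the ranges assumed above, and fewer per group in Period 2, when placebo subjects are split between doses. Within-arm falls will include regression to the mean, so Period 1 results should be read only against placebo. Period 2 has no concurrent placebo, so Week 12 figures are descriptive only. Making the change before unblinding keeps it prespecified.
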